Medical history Presence or absence of other conditions	Patients who had data indicating presence or absence of medical history of other conditions in “161207 medical history (FIX) CRO” are deemed to have other conditions, and patients without such data are deemed to not have other conditions.
Complications Presence or absence of hepatic function disorder	Patients who had data indicating presence or absence of liver disorder in “161207 complication (FIX) CRO” are deemed to have hepatic function disorder, and patients without such data are deemed to not have hepatic function disorder.
Complications Presence or absence of renal impairment	Patients who had data indicating presence or absence of renal disorder in “161207 complication (FIX) CRO” are deemed to have renal impairment, and patients without such data are deemed to not have renal impairment.
Complications Presence or absence of circulatory disturbance	Patients who had data indicating presence or absence of renal disorder in “161207 complication (FIX) CRO” are deemed to have circulatory disturbance, and patients without such data are deemed to not have circulatory disturbance.
Complications Presence or absence of hematologic disorder	Patients who had data indicating presence or absence of hematologic disorder in “161207 complication (FIX) CRO” are deemed to have blood disorder, and patients without such data are deemed to not have hematologic disorder.
Complications Presence or absence of respiratory disorder	Patients who had data indicating presence or absence of respiratory disorder in “161207 complication (FIX) CRO” are deemed to have respiratory disorder, and patients without such data are deemed to not have respiratory disorder.

Name of data	Derivation and calculation method
Complications Presence or absence of other conditions	
Patients who had data indicating presence or absence of complication classified into other detailed classification (diabetes mellitus, gastrointestinal disorder, osteoporosis, malignant tumour, and collagen disorder, and others) in “161207 complication (FIX) CRO” are deemed to have other conditions, and patients without such data are deemed to not have other conditions.
 
In addition, if there is applicable data for Presence or absence of any conditions by “complications including other detailed classification”, patients are deemed as having such conditions and those without such data, they are deemed to not have such conditions.

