BMI	Younger than 18.5 years, 18.5 years or older and younger than 25 years, 25 years or older and younger than 30 years, 30 years or older, unknown
Smoking habit	Absent, present, unknown, not described
Disease duration (years)	Shorter than 2, 2 or longer and shorter than 5, 5 or longer and shorter than 10, 10 or longer, unknown/not described
Reasons for use	Gastro-intestinal Behcet disease, other conditions, unknown, not described
Diagnostic classifications of Behcet disease	Complete type, incomplete type, suspected, others, unknown/not described
Main symptoms of Behcet disease	Recurrent oral mucosa aphthous ulcer, cutaneous symptoms, eye symptoms, ulcer of vulva
Evaluation of main symptoms of Bechet disease	0,1,2,3 Recurrent oral mucosa aphthous ulcer Cutaneous symptoms (erythema nodosum, subcutaneous phlebitis, folliculitis-like skin eruption, acne-like skin eruption) Ulcer of vulva Eye symptoms
Presence or absence of eye symptoms of	There is no symptom: Point for evaluation of main symptoms of Bechet disease is 0

data	Method of dividing hierarchy
Bechet disease	There are any symptoms: Points for evaluation of main symptoms of Bechet disease are 1,2,3 Unknown/not described: Other than above situations
Accessory symptoms of Bechet disease	Arthritis without deformity or rigidity, epididymitis, gastrointestinal lesions characterized by ulcer of ileocecum, vascular lesion, moderate or higher degree central nervous lesion
Presence or absence of accessory symptoms of Bechet disease	There are any symptoms: there are check marks in boxes for each accessory symptom There is no symptom: Other than above
History of allergy	Absent, present, unknown, not described
Tuberculin test or IGRA test	Not implemented, implemented, unknown, not described
HBs antigen	Not implemented, implemented, unknown, not described
HBs antibody	Not implemented, implemented, unknown, not described
HBc antibody	Not implemented, implemented, unknown, not described
HBV-DNA quantitative	Not implemented, implemented, unknown, not described
Complications	Absent, present, unknown, not described
Detailed classification of complications	Liver disorder, renal disorder, circulatory disorder, blood disorder, respiratory disorder, others
Other classifications of complications	Diabetes mellitus, gastrointestinal disorder, osteoporosis, malignant tumour, collagen disorder, others
Medical history	Absent, present, unknown, not described

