## “1.12.1 Distribution of patient characteristics”

Patients included in analysis: Patients included in safety analysis, patients included in efficacy analysis, patients whose survey sheet data was fixed

Objective of analysis: Distribution of patient characteristics is shown

Analysis items: The number of patients included in analysis should be calculated.

The number of patients according to following classifications defined in “11 method of dividing hierarchy of data” and rate of these patients to those included in analysis should be calculated.

Sex, pregnancy/lactation, race, age (years), body weight (kg), body height (cm), BMI (kg/m^2), smoking habit, disease duration (years), reasons for use, diagnostic classifications of Behcet disease, main symptoms of Behcet disease, accessory symptoms of Behcet disease, allergy history, tests for tuberculosis, test for hepatitis B, complications, detailed classifications of complications (liver disorder, renal disorder), medical history, previously used drug/previous treatment, classifications of biological preparations as previously used drug/previous treatment, classifications of drugs other than biological preparations as previously used drug/previous treatment, concomitant drugs, detailed classifications of concomitant drugs, combination therapy, detailed classifications of combination therapy, endoscopy, detailed classifications of endoscopy

In addition, summary statistics should be calculated for following items.

Age (years), body weight (kg), body height (cm), BMI (kg/m^2), disease duration (years)

Notes: Rate of pregnancy/lactation should be calculated as that to female patients.

In addition, breakdown of each item should be represent the rate of patients to the aggregated number of patients corresponding to the item at one-step higher hierarchical level.

(Example: Rate of patients according to detailed classifications of complication to all patients who have complications should be calculated)

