Company should be displayed as name Name of prefecture should be obtained from “Nippon Ultmarc Inc. classification of reassessment”

(5) Abbreviated name of patients

According to GB, “Not applicable” should be used

(6) Sex

According to GB, description should be as male, female, unknown, or not described

(7) Birth date (or age)

Description should be unified to age. According to GB, description should be as ”A + age + "0000""

(8) Distinction between inpatient and outpatient

According to GB, description should be as inpatient, outpatient, unknown, or not described.

(9) Reasons for use

Code, disease name: LLT code and name displayed as LLT of MedDRA should be obtained based on reason for use of this drug described in the survey sheet

(10) Severity before administration

“items not collected” should be applied.

(11) Complications

Presence or absence: “presence or absence of complications” defined in “10.1

Overall”.

The number of complications described: The number of PT codes applied to the complications based on MedDRA should be employed. Complication with the same PT code in one patient should be counted as 1. If there is no complication, “0” should be applied.

Name of complication: It should represent a name of PT based on MedDRA Description should include detailed classification of complications, disease name as complication, and consecutive number of complications in that order. This item should be left as blank space if the number of complication described is “0”.

(12) Administration route

“SC” should be employed.

(13) The maximum dose (daily dose/one time dose)

The one time maximum dose should be employed. According to “Administration status (dosage and administration)” defined in “10.1 Overall”, the maximum value by patients should be employed.

(14) Mean dose (daily dose/one time dose)

Mean one time dose should be employed.

According to “Administration status (total number of administration, total dose)” defined in “10.1 Overall”, “total number of administration/total dose” should be employed.

(15) unit

“MG” should be employed.

(16) The number of administrations per day (the maximum)

“1” should be applied.

(17) Duration of use

According to “Administration status (total number of administration, total dose)” defined in “10.1 Overall”, value for “total number of administration” should be employed.

(18) Concomitant drug

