**“2.9 Incidence of adverse reactions (serious adverse reaction and adverse reaction) by patient characteristics”**

Patients included in analysis: Patients included in safety analysis

Objective of analysis: Incidence of adverse reactions should be shown by patient characteristics and factor analysis should be conducted.

Analysis items: In patients in whom adverse reactions occurred in the period subject to safety analysis, the number of all the patients, the number of patients with serious adverse reactions, and rate of these patients to those included in analysis, the number of the patients with adverse reactions and rate of these patients to those included in analysis, and test provided for the adverse reactions (Fisher’s exact test for nominal scale factors, and Mann-Whitney u test for ordinal scale factors) should be calculated by following patient characteristics:

Notes: Patient characteristics are as follows: Age (years), sex, disease duration (years), complication, hepatic function disorder as complication, renal impairment as complication, medical history, allergy history, smoking habit, self-administration as administration status of this drug, previously used drug/previous treatment, biological preparation adalimumab as previously used drug, biological preparation infliximab as previously used drug, steroid as previously used drug, immunomodulative drug as previously used drug, immunosuppressive drug as previously used drug, oral adrenocortical steroid as concomitant drug, oral mucosa recurrent aphthous ulcer as main symptoms of Behcet disease other than gastrointestinal symptoms, cutaneous symptoms as main symptoms of Behcet disease other than gastrointestinal symptoms, eye symptoms as main symptoms of Behcet disease other than gastrointestinal symptoms, ulcer of vulva as main symptoms of Behcet disease other than gastrointestinal symptoms, arthritis without deformity or rigidity as accessory symptoms of Behcet disease other than gastrointestinal symptoms, epididymitis as accessory symptoms of Behcet disease other than gastrointestinal symptoms, vascular lesion as accessory symptoms of Behcet disease other than gastrointestinal symptoms, moderate or higher degree central nervous lesion as accessory symptoms of Behcet disease other than gastrointestinal symptoms, diagnostic classification of Behcet disease, days until the last date of the administration, and mean daily dose.

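### SAP 10.1 derives the circulatory disturbance flag from the renal disorder data, so it duplicates the renal flag and contradicts the separate classes in Section 11

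*SAP*

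**What the plan says.** Section 10.1 of the SAP defines one presence/absence variable per organ class of complication, each read from the same complication file.

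- Circulatory row: "Patients who had data indicating presence or absence of renal disorder in “161207 complication (FIX) CRO” are deemed to have circulatory disturbance". The negative half of the rule works the same way: with no renal record, the flag is set to absent.
- Renal row, directly above: "Patients who had data indicating presence or absence of renal disorder in “161207 complication (FIX) CRO” are deemed to have renal impairment".
- Respiratory row, as an example of the pattern elsewhere: "Patients who had data indicating presence or absence of respiratory disorder in “161207 complication (FIX) CRO” are deemed to have respiratory disorder". The hepatic and hematologic rows follow the same pattern, each with its own disorder.

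Section 11, under the detailed classification of complications, lists "Liver disorder, renal disorder, circulatory disorder, blood disorder, respiratory disorder, others". Circulatory and renal disorder are therefore two classes.

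No other section gives a different derivation for the circulatory flag, and the revision history in Section 1 records no change to this row.

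**The concern.** The circulatory row has the right name and the right result, but its source condition belongs to another organ. Four of the five named organ rows use their own category; only this one does not. A programmer who follows the text builds a variable that says nothing about circulatory disease and repeats the renal flag.

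At stake is the background information reported for individual patients. Section 3.1 says that the results serve as material for the report to the regulatory authority and for the reassessment application. A complication class that shows renal patients as circulatory, and leaves out patients whose only complication is circulatory, would be a plain factual error in such material wherever the class is printed.

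**Working it through.** There is no figure in the SAP to reproduce and no sample size or test level is involved. The check is one of logic, followed by a trace of where the flag could appear.

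**Step 1: the rule as a function.** Let R = 1 if the patient has a renal disorder record in the complication file and C = 1 if the patient has a circulatory disorder record. The SAP sets the renal flag to R and the circulatory flag also to R. The pattern of the sibling rows and Section 11 imply that it should be C.

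| Patient's records | Flag as written (R) | Flag keyed to C | Result as written |
|---|---|---|---|
| Renal only | present | absent | false positive |
| Circulatory only | absent | present | false negative |
| Both | present | present | correct, by coincidence |
| Neither | absent | absent | correct |

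**Step 2: size in symbols.** Let a be the number of patients with renal only, b with circulatory only, and d with both.

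- Circulatory count under the written rule: a + d, the same as the renal count.
- Circulatory count under the keyed rule: b + d.
- Difference in the count: (a + d) − (b + d) = a − b. It can be zero even when patients are misclassified.
- Patients misclassified: a + b.
- Share of true circulatory patients who are flagged: d / (b + d).

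The SAP gives no values for a, b or d, so none of these can be put into numbers.

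**Step 3: do the misclassified patients reappear elsewhere?** The row for other conditions in 10.1 names diabetes, gastrointestinal disorder, osteoporosis, malignancy, collagen disorder and a residual group. It does not clearly pick up patients with only a circulatory disorder. The overall complication variable does include them, because it comes from a check box on the survey sheet and not from the organ flags.

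**Step 4: which outputs could use the flag?**

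- Table 1.12.1 limits the classes to "detailed classifications of complications (liver disorder, renal disorder". No circulatory line is listed.
- Tables 2.9 and 3.4 test "complication, hepatic function disorder as complication, renal impairment as complication, medical history" and further factors. Circulatory disturbance is not among them.
- Listing 1.4 has retrieval flags for liver disorder and renal impairment, none for circulatory.
- The complication subgroup tables are 2.13.1 (hepatic) and 2.14.1 (renal).
- The listing of patients aged 18 or younger shows complications by MedDRA preferred term code and name.
- Table 2.3 (Appendix 3), item (11), does print a class: "Description should include detailed classification of complications, disease name as complication, and consecutive number of complications in that order". It does not say whether the class comes from the 10.1 flag or directly from the record in the complication file.

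The last item is the only identified route to an output, and it is conditional.

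**The case against.** The strongest reply is that this is a copying slip in a variable that no table, test or subgroup is shown to use. Item (11) of Table 2.3 refers to 10.1 for the overall presence or absence of complications, but not for the class. Its other parts work at the level of the individual record: a MedDRA preferred term name and a count of preferred term codes. On that reading a circulatory complication is still printed under its own name, and the class beside it need not come from the patient-level flag. This stands, and it limits the severity. It does not make the rule right.

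A reader might infer three stronger things that the SAP does not support.

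- *That all patients are affected.* Only those with exactly one of the two disorders are misclassified.
- *That patients with only a circulatory disorder are recorded as having no complication.* Only the circulatory flag is wrong. The overall complication variable, which is the one tested in 2.9 and 3.4, is independent of it.
- *That the error touches congestive heart failure as a primary survey item.* That item is an adverse event category derived from a MedDRA list, and no planned table crosses it with background circulatory disease.

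It could also be said that the slip arose in translation, or that the program never followed it. Neither can be told from the SAP. The sentence is complete and unredacted, so it is not damage from text extraction.

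**Conclusion.** The point holds for the written rule. As stated, the circulatory flag is a copy of the renal flag, which contradicts Section 11. It misclassifies every patient with exactly one of the two disorders and nobody else.

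The planned tests, Table 1.12.1 as listed, the hepatic and renal subgroup tables and the overall complication variable are unaffected. An effect on Appendix 3 item (11), or on any other output that prints the Section 11 class, depends on that class being taken from this flag.

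The conclusion assumes that having such data means that a record of the disorder exists in the complication file, as the sibling rows imply. It says nothing about what was actually programmed. Severity is minor to moderate: the rule is certainly wrong, but no effect on a planned result is established.

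**What to change.** In the circulatory row of Section 10.1, replace the renal disorder condition with circulatory disorder, using the Section 11 class name. Then check the program against the corrected row, and re-derive the flag if the wrong rule was coded. It would also help to state in Table 2.3 item (11) whether the detailed class is taken from the 10.1 flags or directly from the complication file.

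The cost is one phrase in the SAP, one optional clarifying sentence and a program check. Design, data collection and the planned tests do not change.

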## 9. General arrangements for analysis

### 9.1. Handling of missing data

When analysis is conducted, missing data at that time is not complemented. However, entry data compliment may be conducted in some items, and therefore, data complement method is defined in items in Chapter 10 or later chapters if any entry data complement is needed.

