### 9.2. Descriptive statistics

Following values should be calculated for categorical data and quantitative data

Types of data	Data required to be calculated
Categorical data	
The number or rate of patients
 
When rate of patients is calculated, patients with “unknown” and “not described” data should be included in denominator.
 
In addition, breakdown of patients is displayed as rate, the number of

Types of data	Data required to be calculated
	patients including those with “unknown” and “not described” data from high-order items should be used as denominator. When test is performed, patients with “unknown” or “not described” data should be excluded.
Quantitative data	The number of patients, mean value, standard deviation, median value, the minimum value, and the maximum value should be applicable

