### 9.5. Test method

Unknown or not described classification should not be included in test. In addition, test of data by classification is performed, the first hierarchy should be tested in principle. Multiplicity should not be considered.

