Patients who discontinued the administration	If the last date of the final administration of this drug corresponds to following conditions, the patients are deemed to be those who discontinued the administration.

Name of data	Derivation and calculation method
	
Patients who started to receive this drug by August 15, 2013: The start date of the initial administration + less than 1064 days
 
Patients who started to receive this drug between August 16, 2013 and August 15, 2014: The start date of the initial administration + less than 700 days
 
Patients who started to receive this drug between August 16, 2014 and August 15, 2015: The start date of the initial administration + less than 350 days

Presence or absence of reasons for discontinuation	
If patients correspond to those who discontinued the administration and there is at least one check mark in any “Reasons for discontinuation” boxes in “Discontinuation of the survey” section in the survey sheet, the patients are deemed as having reasons for discontinuation and if no description is found in the “Reasons for discontinuation” box in the survey sheet of patients defined as those who discontinued the administration, such patients are defined as patients whose reason for discontinuation is “unknown or not described reason”.

Patients who continue to participate in the survey	
Patients who do not correspond to those who discontinued administration are deemed as patients who continue to participate in the survey.

Presence or absence of complications	
If there is a check mark in a box for complication in “patient information” in survey sheet, such patients are deemed to have complication, and if a column for “presence or absence of complications” is not completed and cannot be assessed, whether patients have complication or not is deemed as unknown or not described, and in any other situations, patients are deemed to have no complication.

Presence or absence of medical history	
If there is a check mark in a box for medical history in “patient information” in the survey sheet, patients deemed to have medical history, and a column for “presence or absence of medical history” is not completed and cannot be assessed, whether patients have medical history or not is deemed as unknown or not described, and in any other situations, patients are deemed to have no medical history.

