Presence or absence of history of allergy	
If there is a check mark in a box for history of allergy in “patient information” in survey sheet, such patients are deemed to have allergy, and if there is a check mark in a box for “unknown about allergy”, whether patients have allergy is deemed as unknown, and if a column for “presence or absence of allergy” is not completed and in any other situations, patients are deemed to have no history of allergy.

Patients with hepatitis B viral infection	
Patients with description as “hepatitis→ viral” in “complication” and “Type B” in “hepatitis virus carrier” in “patient information”, are deemed to be patients with hepatitis B infection. In addition, patients have events corresponding to MedDRA PT code described in “161207 Hepatitis B (FIX) CRO” are deemed to have hepatitis B infection.

Presence or absence of smoking habit	
If there is a check mark in a box for presence or absence of smoking habit in the survey sheet, patients are deemed to have smoking habit. If there is a check mark in a box for absence of smoking habit in the survey sheet, patients are deemed to have no smoking habit. If there is a check mark in a box for unknown about smoking habit in the survey sheet, whether patients have smoking habit or not is deemed as unknown. If a column for “smoking habit” is not completed, whether patients have smoking habit or not is deemed as not described.

Patients in whom deviation from rules for administration of this drug is noted	
Patients who receive this drug at the dose other than “160 mg→80 mg→40 mg/2 weeks”, “only 160 mg”, or “160 mg→80 mg/2 weeks”, deviation is deemed to have occurred.

Presence or absence of self-administration	
If there is at least one check mark in a column for “Self-administration” in “Administration status” in the survey sheet, the patients are deemed to do self-administration. In any other situations, patients are deemed not to do self-administration.

Presence or absence of self-administration error	
If there is a check mark in a box for “self-administration error was present” in the survey sheet, self-administration error is deemed to be present, and if there is a check mark in a box for “self-administration error was absent”, self-administration is deemed to be absent.
 
In addition, regardless of presence or absence of check mark in

Name of data	Derivation and calculation method

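### SAP 10.1 codes an uncompleted allergy field as no allergy, so the 'not described' class listed in Section 11 can never be filled and blanks enter the tests

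*SAP*

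**What the plan says.** The row on history of allergy in SAP Section 10.1 has three branches. A ticked allergy box counts as allergy. A ticked unknown box means that "whether patients have allergy is deemed as unknown". For everything else the rule is that a column which "is not completed and in any other situations, patients are deemed to have no history of allergy".

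Section 11 lists four classes for history of allergy: "Absent, present, unknown, not described".

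Neighbouring rows of 10.1 treat an empty field differently. For smoking, a column that "is not completed, whether patients have smoking habit or not is deemed as not described". For complications, a column that "is not completed and cannot be assessed, whether patients have complication or not is deemed as unknown or not described". The medical history row follows the complications pattern.

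Two sections govern testing. Section 9.5 states: "Unknown or not described classification should not be included in test". Section 9.2 says of the same patients that, when a test is performed, their "data should be excluded", but it keeps them in the denominator when rates are calculated. Section 9.1 sets the default that "missing data at that time is not complemented", and allows exceptions item by item if they are defined in Chapter 10 or later.

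Allergy history is a tested factor for adverse reactions in Table 2.9 and for response in Table 3.4. As a nominal factor it is tested with Fisher's exact test, at a two-sided 5% level without multiplicity adjustment.

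**The concern.** An empty field carries no information about allergy, yet 10.1 turns it into a negative answer. Section 11 expects a class that this derivation cannot produce. A programmer who follows 10.1 and one who follows Section 11 would produce different tables.

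Two outputs depend on the choice. In Table 1.12.1 the *absent* count absorbs the blanks. In Tables 2.9 and 3.4, patients whose allergy status was never recorded join the non-allergic comparison group, although Sections 9.2 and 9.5 are written to keep such patients out of tests. Table 2.9 also has a follow-on table by seriousness, limited to characteristics that reached significance, so the coding could in principle decide whether allergy appears there.

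**Working it through.** **Step 1. Where a blank goes.** The plan states no figure on this point, so there is none to reproduce. The check starts from the text.

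| Item (10.1) | Empty field becomes | Section 11 has a *not described* class? |
|---|---|---|
| Smoking | not described | yes |
| Complications | unknown or not described | yes |
| Medical history | unknown or not described | yes |
| Allergy | no history | yes, but unreachable |

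The *unknown* class for allergy can still be reached through its own tick box. Only *not described* is left empty. Ten items in Section 11 carry exactly these four classes: smoking, allergy, complications, medical history, previous drug/treatment, concomitant drug, combination therapy, endoscopy, self-administration error, and drug used after discontinuation. In 10.1 the other nine all have a route to unknown and/or not described; allergy does not.

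**Step 2. Effect on the tabulated rates.** Let m be the share of blank fields and q the allergy prevalence, with blanks occurring at random and no unknown boxes ticked. Assume q = 20% and m = 20%; neither is in the plan.

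- *Present* = q(1−m) = 0.20 × 0.80 = 16% of all patients under either coding, because 9.2 keeps unknowns in the denominator.
- *Absent*, blanks coded not described = (1−q)(1−m) = 0.80 × 0.80 = 64%.
- *Absent*, as written = 64% + 20% = 84%.

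**Step 3. Effect on the tested difference.** Assume adverse reaction rates of p1 = 40% with allergy and p0 = 25% without; neither is in the plan. Let b be the rate among blanks. As written,

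rate in *absent* = [(1−q)(1−m)·p0 + m·b] / [(1−q)(1−m) + m].

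With blanks left out, the difference is 40 − 25 = 15 points.

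For random blanks, b = 0.20 × 0.40 + 0.80 × 0.25 = 0.28. At m = 20% the *absent* rate is (0.64 × 0.25 + 0.20 × 0.28)/0.84 = 0.216/0.84 = 0.2571, so the difference is 0.40 − 0.2571 = 14.29 points. Over a range of m:

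| Blank share m | Blanks as share of *absent* | Difference as written |
|---|---|---|
| 5% | 6.2% | 14.81 points |
| 10% | 12.2% | 14.63 points |
| 20% | 23.8% | 14.29 points |
| 30% | 34.9% | 13.95 points |

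For blanks that are not random, at m = 20%:

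- b = 5%: (0.16 + 0.01)/0.84 = 0.2024, a difference of 19.76 points.
- b = 50%: (0.16 + 0.10)/0.84 = 0.3095, a difference of 9.05 points.

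The shift is therefore small and towards zero if blanks are random, and can go in either direction if they are not.

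**The case against.** The strongest reply is that the rule may be deliberate. Section 9.1 allows item-specific handling defined in Chapter 10, and the allergy row is in Chapter 10. Defaulting to absent is also common in this plan: self-administration, the medical history and complication subtypes, the drug classes and the Behcet symptoms all work that way, and several of them are tested in the same tables. Section 11 is not an exact map of 10.1 either. Sex, for instance, has one pooled class in 10.1 and two in Section 11.

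Part of this stands. A reader might infer that the allergy rule breaches 9.1, but 9.1 leaves room for such a rule, so that inference is not supported. A reader might also say that it contradicts 9.5. That section acts on the derived class, and a patient derived as *absent* is not in the excluded class. The exclusion is bypassed, not contradicted.

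The reply does not remove the mismatch. Where a default to absent is clearly meant, as for self-administration, Section 11 offers only absent and present. For allergy it offers *not described*. The allergy sentence also reads as if words were lost: the complications and medical history rows use the same frame with the missing clause in place. That makes a drafting or translation slip the likely cause, but the text as it stands still sends blanks to no history.

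**Conclusion.** The point holds as a mismatch between 10.1 and Section 11 that changes who enters two tests. It is of low severity: one exploratory factor among many, with an effect that is probably small if few fields are blank. The plan gives no blank rate, and the prevalence and reaction rates used in the check are assumptions, so the figures show direction and rough scale only.

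Two stronger readings are tempting and not supported. The first is that the rule understates allergy prevalence. Under 9.2 the *present* rate is taken over all patients in the analysis and is the same under either coding; only the *absent* count is inflated. The second is that the rule always dilutes an association. It does so slightly when blanks are random, but the difference can widen or narrow when they are not.

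**What to change.** In the allergy row of SAP Section 10.1, assign an uncompleted column to *not described*, as the smoking row does, and keep no history for the remaining situations. Section 11 then needs no change, and Sections 9.2 and 9.5 exclude these patients from the allergy tests in Tables 2.9 and 3.4.

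The cost is one clause and a tested sample that is smaller by the number of blank allergy fields.
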